Four to six weeks after 8 (or 16) applications of agent (or 4-6 weeks after the last agent application, if off agent before completing the 8 or 16 week cycle), participants will return for an End of Study Visit. They will be assessed for weight, vital signs, concomitant medications, review symptom diary and study calendar with study staff. Paricipants will complete tobacco and alcohol assessment forms and will be given the option to complete a survey about their experiences while participating in the study. Participants who completed participation in the study and were not given the opportunity to complete the survey at that time may do so by telephone, mail or email once verbal consent has been obtained. They will undergo blood and urine collection for future research. In addition, a blood sample will be collected for CBC with diff and CMP and urine will be collected for a urinalysis and urine pregnancy test. They will undergo a colposcopic examination with digital imaging of the cervix. Cervical specimens will be collected for research endpoints and future research. Additional cervical cells will be collected and sent to the institutional pathology lab for Pap smear and HR-HPV testing. Participants will undergo a LEEP or Cold Knife Cone procedure at this time. If participants decline LEEP or are young women with CIN 2 whose standard of care recommendation had been to observe disease for 6 months, then participants will be given the option to first undergo colposcopy-directed biopsy to assess for residual disease. If subjects opt to have colposcopy-directed biopsy first, then subjects will undergo a minimum of 2 cervical biopsies (one will be at the site of previously noted disease, second will be an endocervical curettage) for histopathological confirmation to verify no microscopic disease. If there is histologic confirmation of residual high-grade squamous intraepithelial lesions or cytologic evidence of ASC-H/HSIL, participants will undergo a LEEP or cone biopsy at future clinical visit according to current clinical care recommendations. If they have evidence of regression (i.e., < CIN2 on histology or cytologic evidence of LSIL/ASC-US/NILM), participants will be recommended to return 6 months later to repeat colposcopic examination with Pap smear and HR-HPV testing (to be performed as the standard of care).

Digital photos will be evaluated for repeat assessment and lesion measurement by a board-certified Gynecologist or Gynecologic Oncologist.

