# 7.5 Post-intervention Follow-up Period

Study staff will contact the participant within 2 weeks of receiving pathology reports of the colposcopically-directed biopsies. Women with CIN 1-3 disease will be offered current clinical management. Any participant with more severe lesions, such as adenocarcinoma-in-situ or cancer, will be referred for management by gynecologic oncology.

The study team will collect results from the follow-up cervical exams/procedures/tests performed within 14 months after the End of Study Visit from the medical records for all participants.

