# 8.2 Secondary Endpoints

- 8.2.1 Response to the combination of agent intervention on cervical disease regression (endpoint based on histologic regression from high-grade lesions to low-grade- or no lesions and clearance of high risk-HPV detection) between baseline and study exit visits.
- 8.2.2 Effect of the combination agent intervention on genotype-specific HPV clearance between baseline and study exit visits.
- 8.2.3 Effect of the combination agent intervention on biomarkers of local immune activation (measurement of changes in expression of Toll-like receptors (TLR2, TLR 3, TLR7, TLR8 and TLR9) and T-regulatory cells (Foxp3) and the levels of mRNA expression and the innate (IFN-α2), immune mediating (IFN-Y, IL-10, IL-12), and proinflammatory (IL-1α, -1β, -6, -8, MIP-1α, TNF) cytokine with intravaginal 5-FU and imiquimod between baseline and study exit visits.

The study will also collect specimens for exploratory studies of vaginal microbiome, proteomics and metabolomics to identify factors affecting histologic regression, HPV clearance and immune activation.

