# 13.5 Secondary Objectives, Endpoints, Analysis Plans

The secondary objectives include describing the response (composite endpoint based on histologic regression and clearance of HR-HPV) to intravaginal 5-FU and imiquimod and type specific HR-HPV clearance and measuring changes in the expression of biomarkers of local immune activation (including IFN- $\alpha$ 2, IFN-Y, IL-10, IL-12, IL-1 $\alpha$ , -1 $\beta$ , -6, -8, MIP-1 $\alpha$ , TNF) after treatment with self-administered intravaginal use of 5-FU and imiquimod. The response and type-specific HR-HPV clearance will be reported along with their 95% confidence intervals. For each biomarker, the mean change and the associated standard deviation will be reported. Analyses will be performed on all participants who provide post-intervention specimens for endpoint evaluation. Assume an attrition rate of 15% (for completing intervention and providing post-intervention specimens). There will be at least10 participants available for the secondary analyses. Based on a sample size of 10, it allows us to construct a 95% confidence interval for the overall response and clearance rate, respectively, with a width  $\leq 0.72$ . It also allows us to construct a 95% confidence interval for the overall change in expression of each biomarker with a distance from the mean change  $\leq 0.72$  standard deviations. With an anticipated attrition rate of 15%, we will try to reduce the fraction of participants with missing outcomes as much as possible. Also, multiple imputation techniques will be used to handle missing data. Similar to the primary endpoints, each of the secondary endpoints will be also reported by whether or not the participants continue to the expansion phase.

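### Exit histology comes from excision in some women and from as few as one directed biopsy plus a curettage in others; the analysis neither separates the two nor uses the 14-month results

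*Combined protocol and SAP*

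**What the plan says.** Section 3 makes excision the default at study exit: "Participants will undergo a LEEP or Cold Knife Cone procedure at this time". The exception is "If participants decline LEEP or are young women with CIN 2 whose standard of care recommendation had been to observe disease for 6 months"; in those cases "participants will be given the option to first undergo colposcopy-directed biopsy to assess for residual disease". The minimum sampling on that route is "subjects will undergo a minimum of 2 cervical biopsies (one will be at the site of previously noted disease, second will be an endocervical curettage". Section 7.4 repeats the arrangement, and the schedule in Section 7.1 puts excision and directed biopsy in one row.

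Section 8.2 defines the efficacy endpoint as "endpoint based on histologic regression from high-grade lesions to low-grade- or no lesions and clearance of high risk-HPV detection", without naming the specimen. The Schema lists histological regression as a secondary endpoint in its own right. Section 13.5 states: "Analyses will be performed on all participants who provide post-intervention specimens for endpoint evaluation". Its only planned split is by whether a woman continued into the extension phase. The optional sub-analyses in Section 13.8 concern adherence and protocol deviations.

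Sections 3, 7.1 and 7.5 have the study team collect, for all participants, results of cervical examinations, procedures and tests "performed within 14 months after the End of Study Visit". Section 13 does not mention these results.

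**The concern.** Section 2.1 describes excision as removing 1–3 cm from the transformation zone. Section 4.2.9 excludes only women with more than two quadrants of CIN 3, so disease in up to two quadrants is allowed at entry. One site biopsy plus a curettage does not examine the same tissue as an excision, and a focus of high-grade disease that it misses is read as regression.

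The route is chosen, not assigned. One group offered it, young women with CIN 2, has a favourable natural history: Section 2.1 cites spontaneous regression in 40–58% of CIN 2 and more regression in younger women. Method is therefore mixed with grade and age. With a single arm there is no comparator in which the error could cancel. Section 2.3 places this study before an efficacy trial, and Section 13.1 says extension-phase data will further assess efficacy, so a reader will want to know how many regressions were established by excision.

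**Working it through.** **1. The plan's own figure.** Section 13.5 takes 15% attrition from 12 women (12 × 0.85 = 10.2, so 10) and gives a 95% interval width of at most 0.72. A continuity-corrected normal interval at 50% reproduces it: 2 × (1.96 × √(0.25/10) + 1/20) = 2 × (0.310 + 0.050) = 0.720. The figure covers sampling error only and does not depend on the procedure.

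**2. Formula for the histologic excess.** Take excision as the reference and assume that biopsy does not report high-grade disease where there is none. Let b be the share of evaluated women with biopsy only, r the true regression rate in those women, and f the fraction of their residual high-grade disease that is missed. Then

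excess in the histologic regression rate = b × (1 − r) × f,

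which is never negative. The documents give no value for b, r or f, so all the values below are assumptions.

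| r (biopsy group) | b = 0.3, f = 0.2 | b = 0.5, f = 0.4 |
|---|---|---|
| 0.5 | 0.3 × 0.5 × 0.2 = 0.030 | 0.5 × 0.5 × 0.4 = 0.100 |
| 0.7 | 0.3 × 0.3 × 0.2 = 0.018 | 0.5 × 0.3 × 0.4 = 0.060 |

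That is 3 to 10 points at r = 0.5 and about 2 to 6 points at r = 0.7. The second row matters because part of the biopsy group is expected to regress more often.

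**3. Composite response.** A missed lesion counts as response only if HR-HPV has also cleared, so the excess is multiplied by h, the probability of a negative HR-HPV result in a woman with missed disease. Take h = 0.3 and h = 0.56 for illustration. The second is the HPV-negative share after 5-FU in the earlier trial described in Section 2.2, in all treated women and not in those with residual disease.

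- r = 0.5: 0.030 × 0.3 = 0.009 to 0.100 × 0.56 = 0.056, about 1 to 6 points.
- r = 0.7: 0.018 × 0.3 = 0.005 to 0.060 × 0.56 = 0.034, about 0.5 to 3 points.

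**4. In women rather than points.** With 10 women, b = 0.5, r = 0.5 and f = 0.3, the expected number misread as histologic regression is 10 × 0.5 × 0.5 × 0.3 = 0.75. The chance of at least one is 1 − (1 − 0.075)^10 = 0.54. One woman moves the histologic rate from 5/10 (exact 95% interval 0.19–0.81) to 6/10 (0.26–0.88).

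**5. Is there a check in the plan?** The endpoints in Section 8.2 stop at study exit. ASC-H or HSIL cytology leads to a later LEEP or cone under Sections 3 and 7.4, but no text says whether that specimen changes a response already read from a clear biopsy. The 14-month results could show this, but Section 13 gives them no role.

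**The case against.** **Safeguards.** The biopsy follows colposcopy with imaging. It must include the previously noted site and a curettage, and two samples is a minimum. Section 10.2.2 adds p16 staining, and cytology and HR-HPV testing take place at the same visit. All of this stands. It argues for a lower f but does not make f zero, and cytology does not formally enter the histologic endpoint.

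**Stronger readings that the documents do not support.** A reader might infer that the response rate of Section 13.5 is inflated by the full 3 to 10 points. It is not: that response is a composite, and the full excess applies only to histologic regression. A reader might apply one regression rate to all women; the excess depends on the rate in the biopsy group, which may be higher. A reader might also conclude that Section 13 deliberately treats the two methods as equivalent. It is silent on method, so the fair criticism is that the specimen is unspecified and the rates are combined by default. Finally, the wording "If they have evidence of regression (i.e., < CIN2 on histology or cytologic evidence of LSIL/ASC-US/NILM" might suggest that normal cytology alone makes a responder. That sentence sets the follow-up recommendation, not the endpoint.

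**Scale.** No stated decision depends on this endpoint; the only rule is the DLT threshold in Section 13.4. A few points are small beside an interval up to 0.72 wide. Both are true, but the interval does not express an error that runs in one direction.

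**Limits of the remedy.** The check can only downgrade biopsy-only women. The return visit recommended at 6 months comprises colposcopy, Pap and HR-HPV testing, with no required biopsy. This limits what follow-up can confirm and is why it belongs in a sensitivity analysis.

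**Conclusion.** The point holds for histologic regression and, in weaker form, for the composite. The plan combines two methods of differing completeness, chosen non-randomly, and leaves unused the follow-up results that could test the less complete one. The direction follows from the design once excision is taken as the reference. The size cannot be derived from the documents: about 3–10 points at r = 0.5, or 2–6 points at r = 0.7, for histologic regression under the assumed b = 0.3–0.5 and f = 0.2–0.4, and less for the composite. Only descriptive secondary endpoints are affected. It would go too far to say that an upward bias of known size has been shown, or that the feasibility decision is at risk.

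**What to change.** Leave the procedures and the endpoint definition as they are, and add two items to Sections 13.5 and 13.8.

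1. Report histologic regression and composite response by ascertainment method (excision or directed biopsy), with baseline CIN grade shown. With about 10 women, give counts and make no comparison between methods.
2. Add a sensitivity analysis in which a biopsy-only response becomes non-response if CIN 2 or worse appears in the results collected within 14 months, including a later LEEP or cone prompted by ASC-H/HSIL cytology. Show biopsy-only responders with no later result as unconfirmed, and for the others state what kind of later result was available.

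The cost is a little analysis work on data already collected, with no new visit, sample or participant. The downside is that follow-up comes from routine records and will be incomplete, and a later high-grade result may be new disease. The analysis therefore supports the main estimate and does not replace it.

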# 4. PARTICIPANT SELECTION

# 4.1 Inclusion Criteria

- 4.1.1 Women with biopsy confirmed high grade cervical squamous intraepithelial lesions (i.e., CIN3 lesions, and CIN2 lesions with diagnosis confirmed by positive p16 immunohistochemistry staining) within 12 weeks of Baseline Visit
- 4.1.2 Age 18-45 years
- 4.1.3 Karnofsky ≥70%

4.1.4 Participants must have normal organ and marrow function as defined below:

Leukocytes	$\geq$ 3,000/microliter
Absolute neutrophil count	$\geq$ 1,500/microliter
Platelets	$\geq$ 100,000/microliter
Serum creatinine	$\leq$ the upper institutional limits

4.1.5 Participants must have a negative HIV antibody/antigen test and negative C. trachomatis/N. gonorrhea NAAT.

UAZ2016-08-02

4.1.7 Ability to understand and the willingness to sign a written informed consent document.

#### 4.2 Exclusion Criteria

- 4.2.1 Women treated previously with 5-fluorouracil or imiquimod or other medications for high-grade squamous intraepithelial lesions will be excluded from the study.
- 4.2.2 Concurrent vaginal, vulvar, anal lesions or symptomatic infections.
- 4.2.3 Pregnant or planning pregnancy within the next 6 months, or breastfeeding. Pregnant women are excluded from this study because 5-fluorouracil is an antimetabolite with the potential for teratogenic effects. Because there is an unknown but potential risk for AEs in nursing infants secondary to treatment of the mother with 5-fluorouracil, breastfeeding should be discontinued if the mother is treated with 5-fluorouracil.
- 4.2.4 Inability to speak or read English or Spanish
- 4.2.5 Prior hysterectomy
- 4.2.6 Use of anticoagulant medications
- 4.2.7 Subjects who have a known immunocompromised condition (HIV+, use of immunosuppressive medications or systemic steroids, organ transplant recipients) or autoimmune conditions (e.g. psoriasis, rheumatoid arthritis or other known autoimmune condition).
- 4.2.8 Evidence of invasive anal, vulva, vaginal, or cervical carcinoma; prior LEEP or ablative treatment within 6 months prior to study entry; other invasive malignancies, with the exception of non-melanoma skin cancer, within the last 5 years;
- 4.2.9 Pathologic findings consistent with
  - atypical endometrial cells or serious glandular-cell atypia (atypical glandular cells, favor neoplasia cytology diagnosis)
  - evidence of cervical carcinoma on Pap smear or biopsy
  - more than two cervical quadrants of CIN 3 as visualized by colposcopy
  - nonvisual squamous columnar junction on colposcopy with no concurrent endocervical sampling performed
- 4.2.10 Use of other investigational agents within 6 months prior to enrollment.
- 4.2.11 History of allergic reactions attributed to compounds of similar chemical or biologic composition to 5-fluorouracil or imiquimod.
- 4.2.12 Uncontrolled intercurrent illness including, but not limited to, ongoing or active infection (other than HPV), symptomatic congestive heart failure, unstable angina pectoris, cardiac arrhythmia, or psychiatric illness/social situations that would limit compliance with study requirements.
- 4.2.13 Subjects with known partial or complete dihydropyrimidine dehydrogenase (DPD) enzyme deficiency.

#### 4.3 Inclusion of Women and Minorities

Women and members of all races and ethnic groups are eligible for this trial. Men are not included because they do not have a cervix or vagina.

#### 4.4 Recruitment and Retention Plan

Study participants will be recruited from patients seen at the Protocol PI's UNC OBGYN outpatient clinics, and from outside referring physicians. The Protocol PI is the Medical Director of the UNC Cervical Dysplasia Clinic and Senior Medical Director of all the UNC Obstetrics & Gynecology clinics and will have access to all patients seen in them. These include UNC OBGYN at Hillsborough, UNC OBGYN Weaver Crossing, and UNC GYN Oncology at Rex Hospital in Raleigh. Potentially eligible patients will be identified and contacted about the study. If they express interest in participation, they will present for an in person consent and screening visit. Patients contacted for the study will be listed on the AQUIP enrollment log as required by DCP. Reasons for refusal of study participation will be recorded by the study coordinator and evaluated regularly by the Protocol PI.

Retention will be centered upon follow-up telephone or other contacts (e.g., email or in person). The study team will provide a friendly and comfortable study setting for participants from initial contact through the completion of their study activities. Demands upon the subjects will be minimized to foster comfort while preserving the research goals. Wherever possible, flexibility will be built into the study schedule to promote compliance.

#### 5. AGENT ADMINISTRATION

Intervention will be administered on an out-patient basis. Reported AEs and potential risks are described in Section 6.2.

#### 5.1 Dose Regimen and Dose Groups

The study will have two phases:

- 1. Initiation phase, which will include a total of 12 to 14 participants and applications of 5-FU and imiquimod on alternating weeks for 8 applications. Participants will self-administer intravaginal 5-FU (2 g of 5% 5-fluorouracil, Effudex) once every other week for a total of 4 applications (wks 1, 3, 5, 7). Participants will receive provider-applied commercially available imiquimod cream 5% (12.5 mg imiquimod in 250 mg cream) directly to the cervix once every other week for a total of 4 applications (wks 2, 4, 6, 8).
- 2. Extension phase, which will include no more than the original 12 to 14 participants and continue their participation for applications of 5-FU and imiquimod on alternating weeks for 8 additional applications as described in the initiation phase.

WEEKS (Initiation phase)	1	2	3	4	5	6	7	8	WEEKS (if continuing to Extension phase)	9	10	11	12	13	14	15	16
5-FU (self-applied)	Х		Х		Х		Х		5-FU (self-applied)	Х		Х		Х		Х	
Imiquimod (provider- applied)		Х		Х		Х		Х	Imiquimod (provider-applied)		Х		Х		Х		Х

#### Weekly treatment regimen\*

\*Agent application may be delayed until the end of menstrual cycle if application date occurs during menses. No dose will be applied any sooner than 7 days apart even in the setting of dose delay.

#### 5.2 5-Fluorouracil and Imiquimod Administration

#### 5-FU Administration

- The 5-FU will be supplied to participants in a commercially available multi-dose tube with vaginal applicators for individual use. Participants will be taught how to remove the 5-FU cream from the tube to fill the applicator with 2 grams of the cream prior to each self-application. This method of application has been chosen in order to preserve the shelf-life of the commercially available 5-FU cream.
- Participants will receive phone call, text or email reminders to use the 5-FU cream every other week.
- Participants will self-administer 5-FU on alternating weeks via vaginal applicators. They will perform home pregnancy testing prior to each application.
- 5-FU will be self-applied prior to bedtime. After agent application, the participant will place a tampon in the vagina overnight and remove it in the morning. She will wash the agent preparations off externally and wear panty liners that will be replaced every 2-3 hours or as needed throughout the next day.
- Agent application will be delayed until the end of menstrual cycle if application date occurs during menses.
- Participants will be advised to avoid agent application in circumstances where pregnancy is suspected for any reason by the participant. If this is the case, she will notify study staff.
- Participants will be instructed to dispose the used applicators in trash, away from the reach of other household individuals.
- The participant will enter date and time of drug administration into the study calendar to document adherence to regimen.

#### Imiquimod Administration

- Commercially available imiquimod cream 5% will be applied by the provider directly to the cervix in the clinic on alternating weeks. Urine pregnancy test will be performed prior to each application.
- Visits may be delayed until the end of menstrual cycle if application date occurs during menses. No dose will be applied any sooner than 7 days apart even in the setting of dose delay.
- Date and time of imiquimod application will be documented in the study calendar by the provider.
- After the application, the participant will lay in the supine position for at least 30 min. The participant will then place a tampon in the vagina. Before going to bed, she will remove the tampon and shower to wash any agent preparations off externally and wear a pad during the night. The pad will be replaced every 2-3 hours or as needed throughout the next day.

# 5.3 Run-in Procedures

Not Applicable.

# 5.4 Contraindications

Participants will be informed to avoid intercourse for 48 hours after each agent application. Dual contraception with condoms and another hormonal or long-acting method will be required. Condoms will be recommended for additional contraception, for the prevention of sexually transmitted infections, and to potentially protect male partners from any residual medication.

# 5.5 Concomitant Medications

Women will be excluded if they are using anticoagulants or immunosuppressive medications.

All medications (prescription and over-the-counter), vitamin and mineral supplements, and/or herbs taken by the participant will be documented on the concomitant medication CRF and will include: 1) start and stop date, dose and route of administration, and indication. Medications taken for a procedure (*e.g.*, biopsy) and those used to minimize vulvular irritation or pain should also be included.

